**Table 7-1. Power for dose proportionality assessment,  $\alpha = 0.05$**

Sample size (per arm)	CV	Simple linear model and hypothesis testing approach	Power model and CI approach
N=6	25%	93.3%	98.4%
	35%	93.6%	74.9%
	45%	93.2%	33.3%
N=8	25%	95.0%	99.7%
	35%	95.1%	81.1%
	45%	93.8%	41.8%
N=10	25%	95.5%	99.8%
	35%	95.0%	85.0%
	45%	94.4%	43.5%
N=12	25%	96.1%	99.7%
	35%	93.9%	85.2%
	45%	94.6%	43.6%

Simulation results suggested that either 6 or 12 participants per arm would yield sufficient power for a range of coefficient of variation parameters (25% - 45%) when dose proportionality is assessed using hypothesis testing approach based on simple linear regression model. However, the empirical power associated with the power model and the CI approach is more heavily depend on the value of CV in the relevant range. With  $CV \leq 35\%$ , a reasonable degree of variation given the argument above, we would have  $\geq 81\%$  power to claim dose proportionality with 8 participants per arm. For this reason, in addition to cost and operational considerations, 8 subjects per arm was selected as the minimum size to provide adequate power for the dose-proportionality assessment, our primary objective.

For the secondary objective assessing difference in intracellular TFV-DP and FTC-TP steady state Day 35  $C_\tau$  (pre-dose concentration) between men and women, we assume the mean TFV-DP steady state concentration  $C_\tau$  is 100 fmol/ $10^6$  cells, and the coefficient of variation between people is 35%. Based on the results from Van Belle and Martin (Van Belle and Martin, 1993), we would have only 35% power to detect a 1.5 fold difference (i.e., 100 to 150) between men and women within each dosing arm if an arm has 4 men and 4 women (i.e., a total of 32 participants distributed evenly into four arms, 50% men and 50% women). If dose-proportionality holds, then we would be able to make the comparison between men and women across dosing arms. We then would have 89% power to detect a 1.5 fold difference with a total sample size of 32 (16 men and 16 women) selected for this study. Table 7-2 provides power for a range of CV, sample size and minimal detectable difference. The power would reduce with smaller sample size, smaller minimal detectable difference, and larger CV.

**Table 7-2. Power to detect the minimal detectable difference (in fold) for various sample sizes and coefficients of variance (CV)**

CV	N per group	Minimal detectable X-fold difference		
		1.25	1.5	1.75
0.25	3	0.18	0.48	0.73
	4	0.24	0.60	0.85
	6	0.33	0.78	0.95
	12	0.58	0.97	0.99
	16	0.70	0.99	0.99
	24	0.86	0.99	0.99
0.35	3	0.12	0.28	0.45
	4	0.14	0.35	0.57
	6	0.19	0.49	0.74
	12	0.34	0.78	0.96
	16	0.43	0.89	0.99
	24	0.59	0.97	0.99
0.45	3	0.09	0.19	0.30
	4	0.10	0.23	0.38
	6	0.13	0.33	0.53
	12	0.22	0.57	0.82
	16	0.28	0.69	0.91
	24	0.40	0.86	0.98

## **7.4 Study Arm Assignment**

At the time of consent, subjects will designate whether they will participate in the non-intensive or intensive sampling cohort. Assignment prioritization will go to the intensive sampling cohort. Within each of these 2 cohorts and each gender stratum, enrolled participants will be assigned at random to one of the four study arms in a 1:1:1:1 ratio. The permuted block randomization scheme will not be stratified by site and will be generated and maintained by the HPTN SDMC. For each randomized participant who is not fully evaluable (see section 7.3) an additional participant of the same gender will be enrolled into the same arm and the same cohort (intensive or non-intensive sampling). Details of the randomization system will be in the SSP Manual.

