## SCHEMA

**Purpose:** Describe the dose-proportionality and intra-individual variability of tenofovir diphosphate (TFV-DP) and emtricitabine triphosphate (FTC-TP) at steady-state in healthy human participants taking Truvada® (FTC 200mg/TDF 300 mg) under direct observation.

**Design:** Phase 1, multi-site, open label, randomized, 4-arm, dose-ranging, pharmacokinetic (PK) study.

**Study Population:** HIV-uninfected, healthy, sexually-active volunteers, including both men and women recruited from two sites in the United States (U.S.).

**Study Size:** 32 participants distributed into four 8-person cohorts with 4 men and 4 women per cohort. 16 of the original 32 participants (2 men, 2 women per dosing cohort), will undergo intensive tissue sampling.

**Treatment Regimen:** Research participants will receive doses under the direct observation of study personnel for 5 weeks. Research participants will be enrolled randomly into one of four study arms:

1. FTC 200 mg/TDF 300 mg, one tablet orally once weekly for 5 weeks
2. FTC 200 mg/TDF 300 mg, one tablet orally twice weekly for 5 weeks
3. FTC 200 mg/TDF 300 mg, two tablets orally twice weekly for 5 weeks
4. FTC 200 mg/TDF 300 mg, one tablet once daily for 5 weeks

**Study Duration:** Approximately 12 months total. Accrual will require approximately 6 months. Each participant will be followed for approximately 2 months (screening, treatment, and follow-up).

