### **7.6.2.2 Differences between Men and Women**

Because the genital tracts of men and women differ greatly in terms of anatomy and physiology (e.g. pH differences) as well as drug metabolism, it is feasible that there may be gender-specific differences in the pharmacology of different doses of tenofovir and emtricitabine in different mucosal compartments. Differences in tissue concentrations of these drugs could be relevant in understanding if gender-related differences are detected in intermittent PrEP efficacy trials. Some gender-related differences may be primarily explained by differences in body mass index between men and women, so determining the specific reasons for potential gender-related differences may be challenging with relatively small sample sizes. Men and women will be recruited into the study in equal proportions for comparison. If dose-proportionality is established in the primary objectives, then dose-adjusted Day 35  $C_{\tau}$  concentration differences (each analyte, location, and matrix) between men and women will be tested pooling all research participants using ANOVA. If dose-proportionality is not established in the primary aim, intracellular PK parameters will be summarized by standard descriptive statistics (such as means, medians, and ranges) for each gender within each dose arm. Non-parametric methods may be used to compare  $C_{\tau}$  between men and women. The lack of statistical power of these comparisons due to small sample size is acknowledged.

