#### Processing of samples for PK analysis (measurement of drug levels)

Blood samples will be processed locally to isolate serum and cells of interest. Detailed procedures for processing, freezing, storing, and shipping tissue samples are provided in the SSP Manual.

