### Pharmacology

The HPTN NL will perform all drug testing for this protocol. Drugs will be measured in serum, PBMCs, CD4+ blood cells, total tissue cells, CD4+ tissue cells, tissue homogenate, and luminal (vaginal and rectosigmoid) fluid using assays that have an assay validation report (AVR) and SOP approved by the CPQA. Results from these tests will not be returned to study participants.

As described in Section 5, the following types of specimens will be collected for testing at the HPTN NL:

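### Blood cells are isolated at two sites but the stated power model and gender ANOVA have no site term, which costs avoidable precision and leaves the gender comparison open to site confounding if the gender mix differs by site

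*Protocol*

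**What the plan says.** The Schema describes volunteers "including both men and women recruited from two sites in the United States" and a study of "32 participants distributed into four 8-person cohorts with 4 men and 4 women per cohort". Section 7.4 sets the allocation: within each sampling cohort and gender stratum, "enrolled participants will be assigned at random to one of the four study arms in a 1:1:1:1 ratio". It then excludes site as a stratification factor: "The permuted block randomization scheme will not be stratified by site and will be generated and maintained by the HPTN SDMC". Replacements are matched on gender, arm and sampling cohort, not on site.

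On the laboratory side, section 9.1 states: "Blood samples will be processed locally to isolate serum and cells of interest". Only the drug assay is central (section 9.2): "The HPTN NL will perform all drug testing for this protocol".

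Section 7.3 writes the power model as log concentration regressed on log dose. Section 7.6.1.1 declares dose proportionality if the 90% confidence interval of that slope lies inside 0.64 to 1.36. Section 7.6.2.2 tests dose-adjusted Day 35 concentrations between men and women by ANOVA on all participants pooled, if proportionality holds. Neither model is given a site term. On gender balance, 7.6.2.2 says: "Men and women will be recruited into the study in equal proportions for comparison". No balance within site is set.

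**The concern.** Intracellular concentrations are expressed per million cells (section 7.3), so cell recovery and counting enter the primary endpoint directly. Those steps are done at the sites. A central assay removes assay differences between sites, but not differences in how cells were isolated or counted.

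Two separate consequences follow.

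- **Dose slope.** Arms are randomised, so a site difference does not bias the slope in expectation. It adds variance that a site term would remove. The planned power at CV 35% is 81.1%, so there is little to spare.
- **Gender comparison.** Gender is not randomised. If the two sites recruit different mixes of men and women, a site difference is carried into the men-women contrast. This is secondary objective 2, and section 7.6.2.2 says such differences could matter for understanding gender differences in later efficacy trials.

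**Working it through.** **Inputs from the protocol.** 8 per arm, relative doses 1, 2, 4 and 7, CV 35%, limits 0.64 to 1.36, 90% interval (7.3, 7.6.1.1); 16 men and 16 women; two sites.

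**Assumed inputs.** The protocol gives no site difference, so ratios of 1.25, 1.5 and 2 are taken as a range. The site split is taken as 16:16.

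**1. The plan's own figure.** Simulating the steps in section 7.3 (normal data, log transform, 90% t interval), and counting a replicate with any non-positive draw as a failure, gives 81.7% to 82.0% against 81.1% in Table 7-1. The published figure is reproduced and is not in error.

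**2. Slope precision.**
- Log-scale SD at CV 35%: sqrt(ln(1 + 0.35²)) = 0.340.
- Sum of squares of log dose with 8 per arm: Sxx = 17.1. Base slope SE = 0.340/sqrt(17.1) = 0.082.
- With an even split, a site ratio r adds (ln r)²/4 to the residual variance. SE inflation = sqrt(0.340² + (ln r)²/4)/0.340.
- r = 1.25: sqrt(0.1156 + 0.0124)/0.340 = 1.05.
- r = 1.5: sqrt(0.1156 + 0.0411)/0.340 = 1.16.
- r = 2: sqrt(0.1156 + 0.1201)/0.340 = 1.43.

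Simulated mean interval widths with log-normal data agree: 0.292, 0.324 and 0.399 without a site term, against 0.282 with one (and 0.277 without a term when r = 1).

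Chance imbalance of arms by site moves the slope with SD 0.5 ln r/sqrt(Sxx), which is 0.049 at r = 1.5. This is already inside the widening: sqrt(0.082² + 0.049²) = 0.096 = 1.16 × 0.082. It is the same variance and must not be added again.

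**3. Primary power, using the protocol's simulation with a site ratio added.**

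| Site ratio (assumed) | No site term | Site term | Arms exactly balanced by site, no site term |
|---|---|---|---|
| 1.0 | 82.0% | 81.1% | 82.4% |
| 1.25 | 80.4% | 81.0% | 81.5% |
| 1.5 | 76.4% | 81.2% | 78.7% |
| 2.0 | 61.2% | 80.4% | 71.7% |

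Most of the loss comes from the missing term, not from the lack of stratification: at a 2-fold ratio, balancing arms by site recovers power only to about 72%, while a site term recovers it to about 80%.

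**4. Gender comparison, with no true gender difference.** The apparent gender ratio is r raised to the power (share of women at the site minus share of men at the site).
- 12 of 16 women and 4 of 16 men at one site: exponent 0.75 − 0.25 = 0.5. Ratios 1.25^0.5 = 1.12, 1.5^0.5 = 1.22, 2^0.5 = 1.41. Simulated false-positive rates without a site term are about 13%, 27% and 56%; with one, about 5% to 6%.
- 10 of 16 women and 6 of 16 men: exponent 0.25. Ratios 1.06, 1.11, 1.19. False-positive rates 6% to 8%.
- 8 of 16 each: exponent 0, no bias. The unadjusted test is conservative (3.8%, 2.4% and 0.5%).
- Gender and site coinciding fully: the whole site ratio appears as a gender ratio, and no model can separate the two.

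**The case against.** **Model terms are often left to the SAP.** The SAP is not at hand and may already include site, and section 7.6.2.2 names ANOVA without listing its factors. This stands as a limit: the missing term is shown for the protocol only. But the protocol does write out the power model and the rule based on it, and it mentions weight and creatinine-clearance adjustment and body mass index without mentioning site. Naming a better model is therefore a fair suggestion.

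**Declining to stratify by site is defensible.** This stands. Cohort by gender already gives four strata of 8. Adding site would give eight strata averaging 4.

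**Every site ratio is assumed.** This stands. The protocol leaves standardisation to the SSP manual, requires good laboratory practice and site quality visits, and assays centrally with approved validation. These controls may make the difference small, though nothing shows it to be zero. At 1.25-fold the loss is trivial. At 1.5-fold the total CV is about 41%, still inside the 25% to 45% that section 7.3 explored; only near 2-fold is the loss large.

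**The 12-of-16 scenario is chosen.** This also stands: the protocol neither predicts nor prevents it. The objective is descriptive, and 7.6.2.2 already warns that reasons for gender differences will be hard to establish.

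**The cost of a site term is not uniform.** Vaginal and semen matrices have 8 people each, so the term takes 1 of 6 residual degrees of freedom and cannot be estimated if all 8 come from one site. This limits the fix.

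**Conclusion.** The point holds as a cheap improvement, not as an error in the plan. The dose slope remains valid. Under assumed site ratios of 1.25, 1.5 and 2, at CV 35% and an even site split, omitting site costs roughly 1, 5 and 19 power points against the same model with a site term. The gender comparison is at risk only if the gender mix differs markedly between sites; with a near-equal mix the effect is negligible.

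A reader might infer three stronger things that the document does not support:

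- That the unstratified randomisation biases the dose-proportionality result. It does not; it affects precision only.
- That stratifying arm assignment by site would protect the gender comparison. It would not, because gender is not assigned. The confounding comes from an unequal gender mix by site.
- That a site difference of 1.5-fold or more is to be expected. Nothing in the protocol indicates its size.

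**What to change.** Leave the randomisation as it is. Prespecify site as a fixed effect in the log-scale power model and in the men-women model for the blood matrices (serum, PBMC, CD4+ blood cells). Report enrolment by site, gender and arm, so that a reader can see whether gender and site can be separated.

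For tissue, luminal fluid and semen (8 to 16 people), use the site term only as a sensitivity analysis, and only where it is estimable.

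The cost for blood is one residual degree of freedom, 30 to 29 in the power model, and about one power point if there is no site effect (82.0% to 81.1%). The text change is a line each in 7.6.1.1 and 7.6.2.2, or in the SAP if it does not already have the term.

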## **7.5 Blinding**

There will be no blinding of the study. All of the outcome measures are objectively determined drug concentrations for which there should be minimal risk for bias.

## **7.6 Data Analysis**

### **7.6.1 Primary Analyses**

#### **7.6.1.1 Dose Proportionality**

Dose proportionality will be assessed by a confidence interval approach based on the power model, using Day 35 pre-dose concentration ( $C_t$ ) data from all evaluable participants in Arms 1-4. Dose-proportionality will be declared if the 90% confidence interval of the slope completely falls in the critical interval ( $1 + \frac{\ln(0.5)}{\ln(7)} = 0.64, 1 + \frac{\ln(2)}{\ln(7)} = 1.36$ ). Analyte concentrations assessed for dose-proportionality will include TFV and FTC in fluids and their phosphorylated moieties, TFV-DP and FTC-TP, in cells. TFV-DP and FTC-TP will also be assessed in tissue homogenates. Weight-based or creatinine clearance-adjusted intracellular PK parameters may also be used in evaluating dose-proportionality (as well as secondary outcomes). Biological matrices included in the analysis will include: serum, PBMC, CD4+ blood cells, rectosigmoid and vaginal luminal fluid, semen, and rectosigmoid and vaginal tissue specimens (total tissue cells, CD4+ tissue cells, tissue homogenate) (see Table 7-3).

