**Figure 1-1. Simulation of tenofovir diphosphate (TFV-DP) concentration in PBMCs (y-axis) versus time (x-axis) anticipated with the four different regimens planned for this study: TDF 300 mg daily (blue, QD 300), TDF 600 mg twice weekly (Monday & Thursday, red, BIW 600), TDF 300 mg twice weekly (Monday & Thursday, green, BIW 300), TDF 300 mg weekly (Monday, purple, QW 300); note all regimens are administered as Truvada® (TDF/FTC). Note the minor increase in  $C_{\text{tau}}$  and  $C_{\text{max}}$  between Day 28 and Day 35 where intra-individual variability will be estimated. Simulation parameters are based on data from previous studies (Hawkins et al., 2005; Pruvost et al., 2005; Pruvost et al., 2009). Simulations assume dose-proportionality and do not include intra-individual variation.**

**Figure 1-2. Simulation of tenofovir concentration in blood serum (y-axis) versus time (x-axis) anticipated with the four different regimens planned for this proposal.** The regimens are described in Figure 1-1. Note the near complete overlap in concentration profiles between all regimens on days when the dose is taken. This is due to a very low accumulation index (see text below).

To use the computer modeling methods described above, *two key facts must be determined with regard to the interaction of drug, participant, and regimen: intra-individual variability and dose-proportionality*. Knowledge of these variables is essential for planning future studies that use estimated PK parameters based on individual drug concentrations to evaluate adherence.

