## **2.0 STUDY OBJECTIVES AND DESIGN**

### **2.1 Primary Objectives**

The primary objectives of this study are to:

- Assess dose-proportionality of intracellular TFV-DP and FTC-TP from weekly to daily dosing (Arms 1-4).
- Describe intra-individual variability in intracellular TFV-DP and FTC-TP concentrations at steady-state (comparison of Day 28 and Day 35).

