### **2.3.2 Study Sampling**

Sampling will occur over 7 weeks: at enrollment (pre-dose), pre-dose #2 (Day 1 for treatment arm 4, Day 3 for treatment arms 2 and 3, and Day 7 for treatment arm 1) and Days 7, 14, 21, 28, 35 and 49 to support each of the several objectives as follows:

1. Sample blood serum and blood cells (total cells and CD4+ cells) weekly for 5 weeks (Enrollment and Days 7, 14, 21, 28, and 35) to assess rate of accumulation and dose-proportionality in concentrations of extracellular TFV and FTC and intracellular TFV-DP and FTC-TP.
2. Sample blood serum and blood cells at steady-state (Day 28 and Day 35) to assess intra-individual variability.
3. When participants consent to participate in HPTN 066, they will be offered the opportunity to participate in the intensive sampling cohort (to provide mucosal samples). The slots in the intensive sampling cohort will be balanced by gender, so that there will be two men and two women who will undergo mucosal sampling in each of the four arms of the study. Potential research participants who do not choose to participate in or are ineligible for the intensive sampling cohort will be offered participation in the non-intensive cohort. The study team will sample rectosigmoid, seminal and vaginal fluid, cells, and tissue (in addition to blood) at Days 35 and 49 to compare extracellular concentrations of TFV and FTC and intracellular concentrations of TFV-DP and FTC-TP, and to estimate the elimination rate of drug from these compartments.

The sampling described must occur on the days prescribed given the need to synchronize post-dose time (7 days) across the four regimens. The blood sampling time should precede the established dosing time by no more than one hour. If the participant cannot have tissue sampled as prescribed, sampling should take place within the visit window, described in the SSP. In all cases, there must be accurate recording of sample collection times.

Biopsies will not be performed during menstruation. As such, the timing of the first dose will need to take into consideration menstrual patterns and will be adjusted accordingly.

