### 5.3 Non-Intensive Sampling Visits

Table 5-3. Non-Intensive Sampling Visits (Days 1‡, 3‡, 7, 14, 21, 28, 35, and 49)	
Component	Procedure/Analysis
Administrative	
 
• Review/update locator information
 
• Schedule next study visit
 

Clinical	
 
• Collect interval medical/menstrual history
 
• Review/update concomitant medications
 
• Record/update adverse events
 
• Coagulation tests (Day 28 only, see SSP, intensive sampling cohort only)
 
• Perform directed physical exam
 
• Reinforce counseling 
 
◦ Contraception
 
◦ HIV/STI risk reduction and male condom
 
◦ Protocol adherence, product use/adherence
 
 
 
• Provide male condoms
 

Blood	
 
• Pre-dose #2: single blood draw for accumulation index (Day 1 for Treatment Arm 4, Day 3 for Treatment Arms 2 and 3, Day 7 for Treatment Arm 1)†
 
• Safety testing (Days 14, 28, 35 and 49 only, see SSP)
 
• Hepatitis B testing (Day 49 only, see SSP)
 
• Store plasma (Days 28 and 49 only)
 
• HIV testing (Day 49 only)
 
• Collect blood specimens for PK analysis 
 
◦ Serum
 
◦ PBMCs
 
◦ CD4+ blood cells
 
 
 

Urine	
 
• Collect urine sample (women only, Day 28 and 49 only) 
 
◦ Pregnancy testing
 
 
 

Study Product Supply	
 
• Administer study product (if applicable)
 
• Collect unused emergency dose of participant's prepared study product on Day 28 Visit for all arms. Provide a new emergency dose of participants' prepared study product on Day 28 Visit in Treatment Arms 2, 3, and 4.
 
• Collect unused emergency dose of participants' prepared study product on Day 31 Visit for treatment Arms 2 and 3, and on Day 34 Visit for Treatment Arm 4.
 

\* If indicated (see SSP)

† Sample collection for each cohort should be done no more than 1 hour prior to the second dose for each cohort. These will occur on day 7 (Cohort 1), Day 3 (Cohort 2 and 3), and Day 1 (Cohort 4), as indicated.

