Typical sample sizes for phase I PK studies generally range between 6 and 12 subjects per arm. A number of different approaches have been used to assess dose proportionality in the literature (Gough et al., 1995; Hummel et al., 2009; Smith et al., 2000). We consider the sample size using the following two approaches:

1) fitting a simple linear regression model between the PK parameter (y) and dose

$y = \alpha + \beta \text{dose}$ , where the hypothesis that  $\alpha = 0$  is tested and the lack of fit of the model is generally tested by adding a quadratic term; and

2) using the power model approach to fit  $\log(y) = \alpha + \beta \log(\text{dose})$ , where 90% CI around  $\beta$  is

compared to the limits  $(1 + \frac{\ln(\theta_L)}{\ln(r)}, 1 + \frac{\ln(\theta_U)}{\ln(r)})$ , where  $(\theta_L, \theta_U)$  are the pre-defined limits and  $r$

is the ratio of the highest to the lowest dose. The power model and the CI approach has become more preferred choice in recent years (Gough et al., 1995; Smith et al., 2000), however, Hummel et al. (Hummel et al., 2009) suggested that the choice of bioequivalence default values of  $\theta_L = 0.8$  and  $\theta_U = 1.25$  seems to be impractically strict when applied over a dose range that is more than doubling apart and proposed a more lenient criterion  $\theta_L = 0.5$  and  $\theta_U = 2$ .

The empirical power of both approaches are computed using a simulation study with the following steps:

1. Generate random samples of size n from a normal distribution

$N(\mu = 14 \times \text{dose}, sd = CV \times \mu)$ , where 14 is the weekly dosing Day 35  $C_r$  from Figure 1-1, and dose = 1, 2, 4 and 7 for Arm 1 to 4 respectively.

2. Fit linear regression model  $y = \beta_0 + \beta_1 \times \text{dose} + \beta_2 \times \text{dose}^2$  (Smith et al., 2000) and test for nonsignificant intercept and quadratic terms (Zhou et al., 2006).

3. Fit linear model  $\log(y) = \alpha + \beta \log(\text{dose})$  and compare 90% CI of  $\beta$  with the pre-specified critical interval  $(1 + \frac{\ln(0.5)}{\ln(7)} = 0.64, 1 + \frac{\ln(2)}{\ln(7)} = 1.36)$

4. Repeat steps 1-3 for 1000 times. The empirical power is calculated as the proportion of the replications in which nonsignificant intercept and quadratic term holds for approach 1 or the CI falls entirely within the critical interval for approach 2.

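### The dose-proportionality rule compares Day 35 troughs taken 168, 96, 96 and 24 hours after the last dose as if they should scale with weekly dose; under exactly linear kinetics FTC-TP always fails, and TFV-DP power at CV 35% drops from the stated 81% to about 55%

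*Protocol*

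**What the plan says.** The first primary objective (section 2.1) is: "Assess dose-proportionality of intracellular TFV-DP and FTC-TP from weekly to daily dosing (Arms 1-4". Section 7.6.1.1 turns it into a decision rule: "Dose proportionality will be assessed by a confidence interval approach based on the power model, using Day 35 pre-dose concentration", with proportionality declared when the 90% confidence interval of the slope lies wholly inside 0.64 to 1.36.

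Section 7.6.1.1 does not name the regressor. Section 7.3 supplies it: the simulation sets "dose = 1, 2, 4 and 7 for Arm 1 to 4 respectively", and the limits use ln(7), the ratio of highest to lowest weekly dose. The simulation generates Day 35 troughs with mean 14 × dose. Its result at CV 35% or less, at least 81% "power to claim dose proportionality with 8 participants per arm", is the reason given for the sample size.

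The dosing days come from three places:

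- The Figure 1-1 legend: "TDF 300 mg twice weekly (Monday & Thursday, green, BIW 300".
- Section 2.3.2, on when the second dose falls: "Day 3 for treatment arms 2 and 3, and Day 7 for treatment arm 1".
- Table 5-3, on collecting unused emergency doses: "on Day 31 Visit for treatment Arms 2 and 3, and on Day 34 Visit for Treatment Arm 4".

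Section 2.3.2 also justifies the sampling days "given the need to synchronize post-dose time (7 days) across the four regimens".

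**The concern.** The 1 : 2 : 4 : 7 pattern in section 1.2.2 describes exposure. A trough also depends on how long the drug has decayed since the last dose, and that time differs between arms by up to a factor of seven. A drug with perfectly linear kinetics will therefore show a trough slope above 1, more so the shorter its half-life.

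Two consequences follow. For FTC-TP, half of the first primary objective, the verdict can be read from Table 1-1 before anyone is dosed, and it will look like the non-linear phosphorylation that sections 1.1.7 and 1.2.1 raise as a possibility. For TFV-DP, the power that justifies 8 per arm is overstated.

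The verdict also controls later work. The multi-compartment model (section 1.1.2), the dose-adjusted variability estimate (7.6.1.2) and the pooled comparison of men and women (7.6.2.2) all depend on proportionality being found. The stated power for the last is 89% pooled and 35% within an arm.

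**Working it through.** **Inputs.** Half-lives from Table 1-1: TFV-DP 150 h, FTC-TP 36 h, serum TFV 17 h, serum FTC 10 h. Last dose before the Day 35 sample: Day 28 (Arm 1), Day 31 (Arms 2 and 3), Day 34 (Arm 4), that is 168, 96, 96 and 24 h earlier. Sample size 8 per arm; CV 25, 35 and 45% (section 7.3). Assumption: each dose adds at once to a pool that decays mono-exponentially. This is relaxed in step 5.

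**1. Reproduce Table 7-1.** Draw y from N(14 × dose, CV × mean), regress log y on log dose, and compare the 90% t-interval with 0.6438 to 1.3562. If a replicate with any non-positive draw counts as a failure, all 12 power-model cells reproduce within about 2 points. For 8 per arm the result is 99.5/82/40%, against the stated 99.7/81.1/41.8%.

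**2. Trough ratios under exactly linear kinetics.** Every arm repeats a 7-day pattern five times, so the ratios to Arm 1 are the same on Day 35 as at full steady state. With half-life h:

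- Arm 2 / Arm 1 = 1 + 2^(72/h)
- Arm 3 / Arm 1 = 2 × (Arm 2 / Arm 1)
- Arm 4 / Arm 1 = (2^(168/h) − 1) / (2^(24/h) − 1)

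TFV-DP: 1 + 2^0.48 = 2.39; doubled, 4.79; 1.1735/0.1173 = 10.0.
FTC-TP: 1 + 2^2 = 5; doubled, 10; 24.40/0.5874 = 41.5.

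The protocol's accumulation index gives the same daily-to-weekly ratio, because steady-state trough is (R_ac − 1) times the single-dose peak: 8.526/0.852 = 10.0 for TFV-DP and 1.702/0.041 = 41.5 for FTC-TP, from unrounded values. Neither is 7. By contrast, week-5 AUC by the same superposition is 1 : 2 : 4 : 7 at 36 h and 1 : 1.99 : 3.98 : 6.94 at 150 h, so section 1.2.2 is right about exposure.

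**3. Expected slopes.** Log doses are 0, 0.693, 1.386 and 1.946 (mean 1.006); deviations −1.006, −0.313, 0.380 and 0.940; sum of squares 2.138.

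- TFV-DP: log ratios 0, 0.873, 1.566, 2.303; cross-product 2.485; slope 2.485/2.138 = **1.16**.
- FTC-TP: log ratios 0, 1.609, 2.303, 3.727; cross-product 3.872; slope 3.872/2.138 = **1.81**.
- Serum TFV and FTC, also listed for this rule: about 3.0 and 4.8.

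**4. Power with 8 per arm.** The simulation means should be about 14, 33.5, 67 and 140 for TFV-DP, not 14, 28, 56 and 98.

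| CV | Normal, 1:2:4:7 | Normal, TFV-DP troughs | Lognormal, 1:2:4:7 | Lognormal, TFV-DP troughs |
|---|---|---|---|---|
| 25% | 99.5% | 88% | 100% | 93% |
| 35% | 82% | 55% | 99% | 74% |
| 45% | 40% | 25% | 91% | 56% |

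FTC-TP is declared proportional in 0.0% of trials at every CV under both error models.

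**5. Sensitivity.**

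- Dropping non-positive draws instead of failing the replicate, CV 35%: about 88% falls to 59%.
- 12 per arm, CV 35%: 66% (normal) or 88% (lognormal).
- TFV-DP half-life 100 h, CV 35%: 25% or 33%. At 200 h: 68% or 88%.
- FTC-TP half-life 24 to 60 h: slopes 2.32 to 1.45, at most 0.5% declared. The slope exceeds 1.36 for any half-life below about 73 h.
- Assumed formation half-life for FTC-TP of 12, 24 and 30 h: slopes 1.72, 1.51 and 1.43. It reaches 1.36 only at about 36 h.
- Assumed formation half-life for TFV-DP of 12 and 24 h: slopes 1.14 and 1.11; power at CV 35% about 61% and 70% (normal), 80% and 90% (lognormal).
- Twice-weekly doses on Days 0 and 4 instead of 0 and 3: slopes 1.82 and 1.17.

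**The case against.** The strongest reply is that the rule asks the question the protocol wants answered. Section 1.1.7 defines proportionality over frequency as well as amount of dosing, and section 1.1.4 reads the gap between observed and expected concentration as a rough share of doses taken. For that use, a trough that does not track weekly dose is non-proportional whatever the cause. This stands in part: for adherence monitoring, a failed FTC-TP slope can be a correct answer. But sections 1.1.7 and 1.2.1 also want to detect saturable processes, and a rule that a linear drug must fail cannot do that.

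The 55% is also one cell: CV 35% is the top of the range section 7.3 calls realistic, and the normal generator yields impossible negative concentrations. At CV 25% power stays at 88 to 93%. The expected TFV-DP slope lies inside the limits, so that test is underpowered over part of the range, not invalid. This is fair, but CV 35% is the cell the protocol uses to choose 8 per arm, and at that CV the loss is 25 to 29 points under each error treatment tried.

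The plan has some cover. By-arm comparisons, decay estimates and an optional non-parametric comparison of men and women are foreseen, and two arms share one schedule. None of these changes the declared verdict or the stated power.

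**Conclusion.** The concern holds. The four-arm trough rule gives FTC-TP a predetermined failure (expected slope 1.81 against an upper limit of 1.36). For TFV-DP the expected slope under linear kinetics is 1.16, and the stated 81% power at 8 per arm and CV 35% becomes about 55% on the protocol's generator, or 74% against 99% with lognormal errors.

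The conclusion rests on relative weekly dose being the regressor (inferred from section 7.3 and the ln(7) limits), on the Table 1-1 half-lives, on the dosing days in the Figure 1-1 legend, section 2.3.2 and Table 5-3, and on formation that is quick relative to elimination. For FTC-TP it survives wide variation in these. For TFV-DP the size of the loss varies with half-life, formation rate and error model. The Day 28 to Day 35 within-participant variability is not materially affected.

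The 7-day synchronisation claimed in section 2.3.2 holds only for Arm 1 on the stated dosing days.

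**What to change.** 1. **Table 7-1.** Rerun the power-model column with schedule-correct trough means. Name the error model and say how non-positive draws are handled.
2. **TFV-DP.** Keep the power model and the 0.64 to 1.36 limits, but first divide each trough by its linear-kinetics schedule factor: 1, 2.39/2 = 1.197, 4.79/4 = 1.197 and 10.0/7 = 1.429 at 150 h. Add sensitivity over 100 to 200 h and at the pooled Day 35 to 49 half-life from section 7.6.2.1. State that the adjusted slope tests linear kinetics, and report the raw slope beside it for adherence use.
3. **FTC-TP.** State that failure of the four-arm trough slope is not to be read as non-linear kinetics. Report the dose-normalised Arm 3/Arm 2 ratio with its 90% interval; the schedule is the same and the dose doubled, so no half-life is needed. Attach no 0.5 to 2 pass/fail rule, because over a 2-fold step a ratio of 0.5 is a complete plateau. Keep any half-life-corrected four-arm slope as a sensitivity analysis only: correcting at 36 h when the truth is 24 to 60 h leaves slopes of 1.51 to 0.64.
4. **Serum TFV and FTC.** State that the four-arm trough slopes are uninformative about proportionality. Use Arm 3/Arm 2 only where values are quantifiable: 96 h is 96/17 = 5.6 half-lives for TFV and 96/10 = 9.6 for FTC.
5. **Section 2.3.2.** Reconcile the 7-day post-dose statement with the dosing days given elsewhere.

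The cost is wording, analysis code and one simulation; no new samples or participants. Two limits remain. The TFV-DP correction depends on the half-life: using 150 h when the truth is 100 to 200 h leaves slopes of 1.09 to 0.96, with corrected power at CV 35% of 74 to 82% (normal) or 93 to 99% (lognormal). Arm 3/Arm 2 spans only a 2-fold range, so it does not by itself answer the weekly-to-daily question. Its 90% interval is roughly ×/÷ 1.24–1.26, 1.34–1.40 and 1.45–1.57 at CV 25, 35 and 45%, so moderate non-linearity could be missed.
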